8. TRIAL PROCEDURES

8.1 Participant identification

We will recruit from the general university population at University of Exeter. Posters, emails, websites, presentations, and social media will all advertise the study for students who wish to tackle anxiety and depression. Recruitment of the cohort will follow successful models (e.g., http://www.mappiness.org.uk/, 66,000 participating). Using proven methods, researchers will recruit participants through:

- multiple traditional and social media (posting and advertising on Facebook, YouTube, Instagram, SnapChat, Google, MySpace, Twitter, TikTok, study website, through media influencers/vloggers, etc adjusted by cost/frequency as needed); social media analytics will be used to enhance recruitment;
- app store, Googleplay store;
- email circulars and local promotion (posters, emails, newsletters, signposting by staff) to university departments;
- snowballing approaches;

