7. PARTICIPANT INCLUSION/EXCLUSION CRITERIA

Table 8 Inclusion/Exclusion criteria

Inclusion	Exclusion
Aged 16 or over.	AGED 16<
PHQ9=<9; GAD7=<9	PHQ9>9; GAD7>9
Suicide risk: PHQ9; Q9=<1 and R2=No and R3=	Suicide risk: PHQ9; Q9>1 and R2=Yes and/or R3
No	=Yes
Resident in UK	
Student at the University of Exeter	Past history of psychosis, mania,
	substance/alcohol dependence

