10.2 Outcome measures (Appendix 2)

Table 10 Outcome measures

Measure	Description	Reliability and Validity
SECONDARY OUTCOMES		
Brief Resiliency Scale (BRS; Smith et al., 2008)	6-item participant rated questionnaire assessing ability to on a 5 point scale for each item with anchors —Strongly Agree and Strongly Disagree. Items 1, 3, and 5 are positively worded, and items 2, 4, and 6 are negatively worded. Scored by reverse coding items 2, 4, 6 and adding responses varying from 1-5 for all six items giving a range from 6-30 with total divided by number of questions answered. Interpretation: Low Resiliency=1-2.99; Medium Resiliency=3-4.30; High Resiliency=>4.31.	Commonly adopted measure of resiliency and has been used to rate resiliency in a large number of populations (e.g. University students; cancer) across many countries (e.g. UK, China, Brazil, Germany). Adequate test-retest reliability (.69) with good internal consistency Internal consistency was good, with Cronbach's α ranging from 0.80-0.91 across four populations varying in age. Within the two University student populations Cronbach's α = 8.84-0.87.
Patient Health Questionnaire-9 (PHQ-9; Kroenke et al., 2001)	9-item participant rated questionnaire assessing frequency of symptoms of depression over the last 2 weeks. 4-point scale for each item, with anchors at 0=not at all, 1 = several days, 2= more than half the days, 3 =nearly every day. Unidimensional scale. Available in English, Spanish, German, and Dutch versions.	Leading measure of depression widely used in clinical trials, clinical practice, and as part of the NHS Quality and Outcomes Framework (QOF) for UK primary care, and Improving Access to Psychological Treatments (IAPT) Minimum Data Set (MDS). Cronbach's α =0.89 in primary care, test-retest reliability (ICC) 0.84 after 48 hours. Validation studies indicate positive correlations with measures of functional status (r=0.73), disability days (r=0.39), and symptom-related difficulty (r=0.55) At cut-off of \geq 10, excellent specificity (0.88) and sensitivity (0.88) with diagnoses of major depression by structured interview, replicated in a UK population (sensitivity 0.80; specificity 0.92).

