12.2 Planned recruitment rate

Recruitment of 120 participants into the study across two iterations of intervention delivery (Cohort 1=30 SbRI; 30 DLT; Cohort 2=30 SbRI; 30=DLT) will take place over 28 weeks (June 2023 to December 2023) (originally 1/9-22 to 13/3/23 within a single study site (University of Exeter). Recruitment rate within this timeframe represents a feasibility outcome.

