14.1.1 Risk management during pre-screening

In response to recommendations from our ethical review boards we have now added a pre-screening section to our assessment to allow those with experience of, or symptoms of depression to access help pages linking to sources of support as soon as possible. Participants are given the following automated paragraph and options:

Pre-screening website automated message:

This study aims to examine the effectiveness of a written strength-based intervention based on Cognitive Behavioural Therapy to enhance resiliency in young people that are currently well. If you are currently struggling with depression, traumatic experiences, or suicidal thoughts then the trial would not be right for you and specialist help would be the best option. If these issues are affecting you now then we would urge you to reach out to family, friends, or your family doctor/general practitioner. Click the relevant button to below for some links to relevant helpful information and support services available to you.

- I would like to learn what depression is
- I am having suicidal thoughts at the moment
- I have depression now
- I have experienced a traumatic experience in the last month
- I do not have depression or experienced a traumatic experience in the last month and would like to take part in the trial
- I do not want to take part

Each of the options is linked to help pages. If participants access the help pages on current depression, or risk then they are excluded from the trial. Their contact details have not been taken at that stage so they cannot be contacted.

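### Section 8.1 directs the advertising at students wanting help with anxiety or depression, while sections 7 and 14 describe a trial for students who are currently well; this is likely to raise screen-outs and cloud part of the primary feasibility outcome

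*Protocol*

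**What the plan says.** Section 8.1 of the protocol first gives the source population: "We will recruit from the general university population at University of Exeter". It then says that the print, e-mail, web, live and social-media channels "will all advertise the study for students who wish to tackle anxiety and depression".

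The inclusion column of the criteria table in section 7 requires "PHQ9=<9; GAD7=<9", and scores above 9 are listed as exclusions. Section 10.2 gives the meaning of the PHQ-9 threshold: a score of 10 or more is reported to have "excellent specificity (0.88) and sensitivity (0.88) with diagnoses of major depression by structured interview".

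Section 14.1.1 sets out the pre-screening page. It describes the aim as "to enhance resiliency in young people that are currently well" and continues: "If you are currently struggling with depression, traumatic experiences, or suicidal thoughts then the trial would not be right for you". The automated messages in sections 14.3.1 and 14.4 say much the same to people who are screened out: the study concerns resiliency and prevention, does not treat present difficulties, and does not suit anyone who is depressed now.

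Feasibility is the primary outcome (study summary in section 5, and section 12.5). The feasibility outcomes table in section 10.1 counts people who reach the website, complete screening, are screened out (with reason), consent and are randomised. Section 12.2 adds: "Recruitment rate within this timeframe represents a feasibility outcome".

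**The concern.** The sentence in 8.1 reads like an invitation to a treatment study, whereas the rest of the protocol describes prevention in people who are not unwell. A student who answers an invitation to deal with depression is more likely than a student picked at random to score above 9. That student then meets a page or an automated message saying that the trial is not suitable.

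Two things are at stake. The first is interpretation. A feasibility trial exists partly to learn how many people must be reached and screened to randomise a given number. If the message attracts a different group from the one the criteria admit, the observed yield reflects that mismatch as well as interest in the intervention. The second is the burden on students who come forward for help that the study does not offer.

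**Working it through.** **No plan figure to reproduce.** Section 12.1 states that there is no sample size calculation, and no expected eligible or screen-out share is given anywhere. The only related arithmetic is in section 12.2: 2 cohorts × (30 + 30) = 120, which agrees with the target. The point therefore rests on comparing the texts.

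**Side by side.**

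| Place | Who the study is for |
|---|---|
| 8.1, source population | students in general at one university |
| 8.1, advertising | students wanting to address anxiety and depression |
| 7, criteria table | PHQ-9 ≤ 9 and GAD-7 ≤ 9 |
| 14.1.1, pre-screening page | young people currently well; not those struggling with depression |
| 14.3.1 and 14.4, screen-out messages | resiliency and prevention; not the currently depressed |

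The advertising line stands apart from the criteria and from both sets of section 14 messages.

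**Overlap.** A student with a PHQ-9 of, say, 7 may want to address low mood and is eligible. The conflict is therefore partial: the advertised group includes people on both sides of the cut-offs.

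**Route to the outcome.** The counts in section 10.1 from website access to randomisation, and the recruitment rate in section 12.2, all depend on who responds to the adverts. Group attendance, questionnaire completion and use of support are further feasibility outcomes, recorded after randomisation and less directly affected.

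**How far the safeguards reach.** Section 10.1 asks for screen-outs with reason and by demographics. Under 14.1.1, a visitor who opens the help pages on current depression or risk is excluded before contact details are taken, and the schedules in 8.11 and 10.3 place demographics at screening. Such visitors may therefore appear only in the website-access count, or as screen-outs that cannot be broken down by demographics.

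**Sensitivity to the eligible share (assumed values).** Let *e* be the share of screened people who are eligible, and assume that every eligible person consents. Screened = 120 / *e*; screened out = 120 / *e* − 120; weekly screening = (120 / *e*) / 28, using the 28 weeks in section 12.2.

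| *e* (assumed) | Screened | Screened out | Per week |
|---|---|---|---|
| 0.8 | 150 | 30 | 5.4 |
| 0.6 | 200 | 80 | 7.1 |
| 0.4 | 300 | 180 | 10.7 |
| 0.2 | 600 | 480 | 21.4 |

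This shows that the counts move a great deal with the composition of responders. It does not measure the effect of the wording: that would need *e* under the present message and *e* under an aligned one, and the protocol gives neither.

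**The case against.** The strongest reply is that 8.1 contains one clause about the intended audience and no advert copy, that the recruitment base is the general student body, and that sub-threshold symptoms are the natural territory of indirect prevention, which section 1 illustrates with insomnia in people with sub-threshold depression. The pre-screening page states the true aim early, the information sheet comes before the screening measures (section 8.3), excluded students are directed to help, and section 10.1 keeps access, screening, screen-out reasons, consent and randomisation as separate counts. The effect would thus be partly visible.

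Much of this stands, and it rules out several stronger readings that a reader might infer:

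- *The adverts target exactly the group that the criteria remove.* They do not; the groups overlap.
- *The adverts say nothing of resiliency.* The clause does not mention it, but the adverts themselves are not in the protocol.
- *The wording deters well students.* Section 1 names stigma as a leading barrier to seeking treatment, which makes this plausible, but nothing in the protocol shows it for this message.
- *The rates will not transfer.* That depends on how a later trial advertises, which is unknown.
- *Screening and recruitment rates are the primary outcome.* They are only part of it; section 12.5 also covers acceptability.

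The reply does not remove the inconsistency. The safeguards act after the message has drawn people in, and the losses at pre-screening are only partly described.

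**Conclusion.** The inconsistency is real and lies in current text: the audience named in 8.1 does not match the one defined in section 7 and stated in section 14. Followed as written, 8.1 is likely to increase screen-outs and to make the access, screening and recruitment counts a less clear guide for a definitive prevention trial. The direction is a reasonable inference, resting on the assumption that people who respond to a message about anxiety and depression score higher on average than students at large. The size cannot be derived from the documents, and the table of assumed shares should not be read as an estimate of it. Confidence is high for the textual mismatch and moderate for its consequence. It is worth correcting because the remedy is cheap and the affected counts are among the things this trial is run to learn.

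**What to change.** Reword the clause in section 8.1, and the advert copy for every channel, so that both match sections 7 and 14.1.1. One possible wording: *for students who are currently well and want to strengthen their ability to bounce back from the demands of university life*. This suits the choice recorded under modifications in section 9.1, where the team took the word resiliency out of the intervention's title and used it less in the text. The eligibility criteria and the risk procedures need no change.

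Cost: one sentence, revised advertising materials and an ethics notification of those materials. Response to the adverts may be somewhat lower, which matters for a target of 120 in 28 weeks, although a larger share of those who respond should be eligible.

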8.2 Screening

Participants will be screened by an EDC system set-up and managed by Exeter CTU for university students - those under 16 will automatically be screened out pre-assessment. Website users who report having current risk will be taken to the feedback screen where they will be advised that we are sorry to hear that they are feeling that way, to please contact their GP and to give them sources of online help and support.

8.3 Consent

We anticipate that university students will be autonomous independent young adults who are legally recognised as being at or above the age of majority and able to provide their own informed consent to their participation in research (aged 16 or over for the UK).

Young people will be initially routed to or seek out the study website and will be provided with the participant information sheet, consent form A and data protection policy to review on the trial electronic platform, prior to completing screening measures. There will be a check box at the bottom of the information sheet which participants will need to check before they can sign the consent form. Participants will then be asked to read, date, and electronically sign consent form A and provide their contact details. Consent form A asks for consent to undertake the assessment and confirmation that the participation understands the nature of the study.

When consent is given, they will be assigned a screening ID number and automatically be emailed a copy of the consent form, information sheet and data protection /privacy policy or given the option to download these documents. The recruit will then be asked to complete brief background screening measures to determine eligibility on the online screening website. Non-excluded recruits can stop and save their assessment at any time and be emailed a link to return to the assessment. The participant will have 2 weeks in which to be able to return to their part completed assessment. After this time, they would need to start the assessment again if they wanted to take part.

If a participant completes the screening assessment and is eligible for the trial, then they will be presented with consent form B1 which asks them to consent to taking part in the trial. Recruits are advised that they can take time to consider taking part and can save their assessment whilst they do so.

On completion of consent form B1 participants are then asked to complete the full baseline assessment measures. Once this has been completed, the recruit is randomised and will be given a unique study participant trial number, and they are informed that they have completed the baseline assessment and that they will be contacted to be informed of the outcome of the randomisation.

All participants will be given the option to seek further information from the research team, with contact details to the relevant research team provided (email, and/or telephone number as available). This information will be provided on all versions of the information sheet and on the help menu of the study website.

8.4 The randomisation scheme

The feasibility with embedded RCT will follow MRC Complex Interventions Guidelines and relevant CONSORT reporting requirements with a pre-registered trial protocol. Randomisation will be in equal allocation (e.g. 1:1) using independent computerised randomisation. Random selection to the 2 arms (sbLICBT vs delayed treatment control) will be conducted automatically by means of a secure service created and managed by the Exeter Clinical Trials Unit (CTU) in conjunction with the trial statistician. This will be independent of the trial researchers.

8.5 Protection from bias

We will adopt prior registration and publication of the trial protocol. Independent web-based computerised randomisation will be conducted to ensure generation of an unpredictable allocation sequence and concealment of participant allocation and of allocation sequence and prevent selection bias and confounding. We will use standardised self-report outcome measures with data collected

automatically through the website. The use of self-administered measures will eliminate observer bias. A detailed statistical analyses plan will be prepared before any analysis is conducted. The trial statistician will remain blinded to group allocation until the main data analyses have been undertaken and interpretation of the trial results have been agreed by the relevant committees. Attrition bias will be minimised by having robust trial procedures to prevent data loss such as email, text, and phone reminders to encourage follow ups.

8.6 Method of implementing the randomisation/allocation sequence

Participants will be randomised by a web service which interfaces with the EXCTU EDC system and database. This will be an automated process. The EXCTU database will send an unblinded team member (administrator/therapist) indicating when an individual [by study ID] has been randomized to the active intervention. This team member will then access the relevant details in the EXCTU database and manually set up the participant in the internet platform using administrator rights via the internet platform dashboard. A system automated email will be sent to the participant indicating the condition to which they are randomised, informing them what to expect, date of sbCBT group to next intervention arm and asking the participant to confirm receipt by return of email to unblinded team member. The team member will send up to 6 reminder emails to any participant that has failed to confirm receipt.

Failure to receive confirmatory email: the relevant unblinded team member will also be able to monitor if the participant has accessed the intervention and check if there are any difficulties and encourage to sign-up.

Detailed procedure for randomisation:

- 1. Participants are block randomised (30 participants per arm) into the 2 arms (DTC control versus sbLICBT) on an intention-to-treat basis.
- 2. Block randomisation will continue until 120 participants (6 iterations of 60 participants) are randomised.
- 3. The system must record the allocation and the date randomised.
- 4. The trial manager and at least one other researcher remain blind to the allocation; the participant will be aware of which intervention received. The practitioner / administrator will be unblinded in order to set-up participant on internet platform.
- 5. On successful randomisation, a finish page is displayed with a message telling the participant to look for an email message from the trial team.

8.7 Blinding

The follow up data will be routinely collected online using the website/EDC system (and the reminders for this will be sent out automatically by email from the EDC system). This will prevent the follow up results being affected by the site researcher. Trial researchers who will be blind to treatment allocation include the Chief Investigator and Trial Manager. The Trial Manager will be in direct contact with participants to answer technical queries. The trial therapists will be unblinded and will be in direct contact with participants to follow up risk. It is possible that a site researcher could become unblinded during those (infrequent) conversations if the participant mentions details of the intervention and this will be recorded as part of the feasibility focus.

Should a blinded site researcher become unblinded then this will be logged as an unblinding and any telephone-based chasing of follow up data for that participant in future will be conducted by another blinded researcher at the site (if available). Therefore, only blinded site researchers will attempt to collect the primary outcome measures by telephone if the participant is unwilling to use the screening website for this purpose. Unblinded site researchers will not discuss information relating to condition with blinded site researchers. During any contact with participants the blinded site researcher will remind them not to divulge to which condition they were allocated. In the event that there are no

unblinded researcher at a site and telephone collection of follow up primary outcome is possible, this data will be collected, but will be logged and clearly marked as 'collected unblinded'. This will allow the statisticians to control for this in their analysis. The statisticians will be blinded to intervention until the analysis is done and they are interpreting the results.

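### Section 8.7 sets the unblinded-collection flag on the reverse of the condition it is meant to record, and the flag's suggested use in analysis needs limits because it arises after randomisation

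*Protocol*

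**What the plan says.** Follow-up is online. Under Protocol section 8.10, people who do not answer email and text prompts at 6 and 12 weeks are telephoned for the primary outcome measures only. Section 8.7 governs who may call:

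- The general rule is that "only blinded site researchers will attempt to collect the primary outcome measures by telephone".
- A researcher may become unblinded in conversation "if the participant mentions details of the intervention". This is logged, and later telephone chasing of that participant "will be conducted by another blinded researcher at the site (if available").
- The exception begins "In the event that there are no" and continues "unblinded researcher at a site and telephone collection of follow up primary outcome is possible, this data will be collected". Records obtained in this way carry a label saying that collection was unblinded.
- The stated purpose of the mark is: "This will allow the statisticians to control for this in their analysis".

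Section 8.6 makes the practitioner/administrator unblinded by design and keeps the trial manager and at least one other researcher blind. The protocol names no model in which the mark would be used.

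**The concern.** The exception has to cover the situation that the preceding sentences leave open: a researcher has been unblinded and no blinded colleague can take the call. As written it covers the opposite situation. The mark is made at the time of the call, so a record labelled by the wrong rule may not be recoverable later, and a statistical analysis plan cannot repair it.

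The second issue is the use to which the mark is put. It does not exist at randomisation. It can arise only in people who needed a telephone call, and one route to unblinding is a participant talking about the intervention, which may be more common in one arm. Adjusting a randomised comparison for a variable of this kind can introduce bias. The comparison is exploratory (section 12.6.2), but section 12.1 says the data will inform the sample size of a later definitive trial.

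**Working it through.** **The trigger.** No arithmetic is needed; compare the intended and literal rules.

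| Situation | Mark the general rule calls for | Mark under the literal text |
|---|---|---|
| A blinded researcher makes the call; no one at the site is unblinded | none | marked as collected unblinded |
| An unblinded researcher makes the call; no blinded one is available | marked | none, because an unblinded researcher is present |

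The result depends slightly on whether the practitioner/administrator counts as a site researcher. Section 8.8 speaks of a site researcher other than that person, which suggests they do. The literal condition would then hardly ever be met, and the calls of interest would go unmarked. If they do not count, the condition is met in the ordinary state of the trial, when nobody on the research side has been unblinded, and ordinary blinded calls get the label. Both readings defeat the purpose.

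**The use of the mark.** The protocol gives no figure to reproduce: section 12.1 has no sample size calculation, and no effect size or SD is stated. The documents supply 120 participants and 1:1 allocation, hence 120 / 2 = 60 per arm. Everything else here is an assumption: outcome SD 1 (higher is better), true effect 0, marking rates by arm as shown, an unmeasured trait explaining 30% of outcome variance, log-odds of marking −1 per SD of that trait where they are linked, and a score shift of 0 or 0.3 SD when collection is unblinded. Rates are those at the average trait value. Bias in SD units over 8,000 simulated trials:

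| Marked, DTC / sbLICBT | Linked to trait | Shift | Unadjusted | Adjusted for mark | Marked records excluded |
|---|---|---|---|---|---|
| 10% / 10% | yes | 0 | 0.00 | 0.00 | 0.00 |
| 2% / 15% | no | 0 | 0.00 | 0.00 | 0.00 |
| 2% / 15% | yes | 0 | 0.00 | 0.08 | 0.07 |
| 5% / 30% | yes | 0 | 0.00 | 0.12 | 0.11 |
| 2% / 15% | no | 0.3 | 0.04 | 0.00 | 0.00 |
| 5% / 30% | no | 0.3 | 0.08 | 0.00 | 0.00 |
| 2% / 15% | yes | 0.3 | 0.05 | 0.08 | 0.07 |
| 5% / 30% | yes | 0.3 | 0.08 | 0.13 | 0.12 |

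The sampling SD of the contrast is about 0.18 to 0.19.

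**A closed-form check.** Let a share p of each arm be reached by telephone, with outcome d for them and 0 for the rest. Let f be the share of calls marked and q = p·f the marked share of an arm (subscript 1 for sbLICBT, 0 for DTC). With true effect 0 and no shift:

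- coefficient of the mark: b = d(1 − p)(q1 + q0) / [q1(1 − q1) + q0(1 − q0)]
- adjusted arm coefficient: −b(q1 − q0)
- arm difference after exclusion: d(p − q1)/(1 − q1) − d(p − q0)/(1 − q0)

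For p = 0.2, d = −0.5, f1 = 0.5, f0 = 0.1: q1 = 0.10 and q0 = 0.02, so b = −0.5 × 0.8 × 0.12 / (0.0900 + 0.0196) = −0.438. The adjusted coefficient is 0.438 × 0.08 = 0.035. Exclusion gives −0.0556 + 0.0918 = 0.036. With f1 = 0.8 the two are 0.065 and 0.068. With p = 0.3 and d = −0.8 they are 0.077 and 0.082 (f1 = 0.5), and 0.150 and 0.160 (f1 = 0.8). Exclusion is no better than adjustment.

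**The case against.** The trigger is a one-word slip whose intent is clear from its context. That is fair, but staff follow the rule as written when they label a call.

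The case against the statistical part is stronger, and most of it stands.

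- **No covariate is fixed.** Controlling for the mark could mean a labelled sensitivity analysis, and section 12.3 defers detail to a statistical analysis plan.
- **Dependence on arm is inferred.** The protocol does not state it. Under section 9.2 the control arm receives the intervention once the intervention arm has finished its 6 weeks, so by week 12 control participants may have it to mention too.
- **Marking should be rare.** On the intended reading it needs an unblinded caller and no blinded replacement. Section 8.7 calls the unblinding conversations infrequent and has callers remind participants not to divulge their allocation. If no replacement is available 10% to 25% of the time (an assumption), multiplying f1 and f0 by 0.10 to 0.25 brings the closed-form result down to about 0.003 to 0.03 SD.

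A reader might infer that the comparison is unbiased without the mark and biased with it. That does not follow. If unblinded collection itself shifts scores, which is the reason for having a mark, the unadjusted contrast is biased when marking differs by arm, and adjustment can remove that bias.

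A reader might also take section 8.5, "The use of self-administered measures will eliminate observer bias", as a false claim about the telephone route. The sentence follows one on data collected automatically through the website and concerns self-administered measures, so it does not clearly reach telephone collection.

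**Conclusion.** The trigger in section 8.7 is wrong as written and contradicts the rule it qualifies. This rests on the text alone and needs no assumption.

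The point on analysis holds as a caution. Adjusting for the mark can bias the between-arm contrast if the mark depends on arm and also shares causes with outcome. If it depends on arm only and unblinded collection leaves scores unchanged, adjustment does no harm. If unblinded collection shifts scores and there is no shared cause, adjustment helps. The documents give no telephone rate, unblinding rate or outcome difference for telephone responders, so neither the size nor the sign of the net effect can be fixed. All the values calculated above are smaller than the contrast's sampling SD.

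The consequence is minor. The primary analysis is feasibility and acceptability (section 12.5), and only telephone records are affected. The correction is still worth making because it is cheap and protects data that must be labelled correctly at the time of the call.

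**What to change.** 1. In section 8.7, change the condition for the exception to there being no blinded researcher available at the site, and word it as an exception to the rule that only blinded researchers call.
2. For every telephone assessment, record the mode of collection and the caller's blinding status, and report both by arm. Section 8.7 already treats unblinding as part of the feasibility focus.
3. Replace the closing remark about statistical control with text such as: 'The flag will not enter the main between-arm comparison. Any analysis that adjusts for flagged records or excludes them will be labelled a sensitivity analysis, with a statement that neither approach is free of post-randomisation selection bias.'

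The cost is a few sentences and one small table. The first two changes need to be in place before the telephone assessments they cover, because blinding status is hard to reconstruct afterwards.
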